5.3 Exclusion Criteria

Subject meeting any of the following criteria will not be eligible to participate in the study:

1. Females who are pregnant or breastfeeding.
2. Any known allergies to any of the components of B/F/TAF.
3. Treatment with another investigational drug within three months of enrollment.
4. Abnormal hematological and biochemical parameters at screening, including:
 - a. Absolute neutrophil count (ANC) < 750 cells/mm³.
 - b. Platelets < 50,000/mm³.
 - c. Hemoglobin < 8.5 g/dL.
 - d. AST or ALT of > 5 times upper limit of normal (ULN).
 - e. Estimated GFR < 30 mL/min/1.73 m².
 - f. Total bilirubin > 1.5 times ULN.
5. Previous or current history of malignancy, other than cutaneous Kaposi's sarcoma, basal cell carcinoma, or resected, non-invasive cutaneous squamous cell carcinoma.
Note: Those with a history of malignancy who are in remission for two or more years may be included in the study.
6. An opportunistic illness indicative of stage 3 HIV diagnosed within the 30 days prior to screening.
7. Subjects experiencing decompensated cirrhosis (e.g. ascites, encephalopathy, or variceal bleeding).
8. Acute hepatitis in the 30 days prior to study entry.

9. Active tuberculosis infection.
10. Subjects receiving ongoing therapy with any medications contraindicated for co-administration with B/F/TAF FDC, including but not limited to the following medications in the table below:

Drug Class	Prohibited Agents [#]
Antiarrhythmic Agent	Dofetilide
Anticonvulsants	Phenobarbital, Phenytoin, Carbamazepine, Oxcarbamazepine
Antimycobacterials	Rifampin, Rifapentine, Rifabutin
GI Motility Agents	Cisapride
Herbal/Natural Supplements	St. John's Wort, Echinacea
Miscellaneous Agents	Mitotane

[#] Administration of any of the above medications must be discontinued at least 30 days prior to the Day 1 visit and for the duration of the study.

11. Current alcohol or substance use that in the opinion of the investigator may interfere with subject study compliance.
12. Any other clinical conditions that in the opinion of the investigator would make the subject unsuitable for the study or unable to comply with the dosing requirements.

6 STUDY INTERVENTION

6.1 Study Assignment

This is an open-label study and all eligible subjects will receive fixed dose combination bictegravir/emtricitabine/tenofovir alafenamide taken one pill once daily oral treatment.

6.2 Method of Assignment to Study Intervention

This is an open-label one-arm study.

6.3 Study Drug, Materials, and Supplies

6.3.1 Formulation, Packaging, and Labeling

Bictegravir 50 mg/Emtricitabine 200 mg/Tenofovir alafenamide 25 mg tablets are capsule-shaped, film-coated purplish-brown, debossed with "GSI" on one side of the tablet and "9883" on the other side of the tablet. Each tablet core contains 50 mg of bictegravir, 200 mg of emtricitabine, and 25 mg of tenofovir alafenamide. In addition to the active ingredients, the B/F/TAF tablets contain croscarmellose sodium, magnesium stearate, and microcrystalline

cellulose. The tablet cores are film-coated with iron oxide red, iron oxide black, polyethylene glycol, polyvinyl alcohol, talc, and titanium dioxide.

The B/F/TAF tablets are packaged in white, high-density polyethylene (HDPE) bottles. Each bottle contains 30 tablets, silica gel desiccant, and polyester packing material. Each bottle is enclosed with a white, continuous thread, child-resistant polypropylene screw cap with an induction-sealed and aluminum-faced liner.

6.3.2 Storage Handling and Preparation

Study drugs should be stored at room temperature of 25°C (77°F); excursions are permitted between 15°C and 30°C (59°F and 86°F). Storage conditions are specified on the label. Until dispensed to the subjects, all bottles of study drugs will be stored in a securely locked area, accessible only to authorized site personnel.

To ensure the stability and proper identification, study drug(s) will not be stored in a container other than the container in which they were supplied.

Bottles will be relabeled by the Investigational Pharmacist as prescribed to each study subject after consent is given and subjects are found to be eligible.

Consideration should be given to handling, preparation, and disposal through measures that will minimize drug contact with the body. Appropriate precautions should be followed to avoid direct eye contact or exposure through inhalation when handling.

6.3.3 Final Disposition of Clinical Supplies

At the end of the study, final study drug supply and accountability records will be reconciled as to drug shipped, drug consumed, and drug remaining. Any discrepancies noted will be documented.

Subject accountability for study drug will be ensured through subject interview (during visits), diaries, and study drug reconciliation at selected visits before dispensing drug supply for the next visit interval. At certain clinic visits, subjects will be asked to return any unused study drug to the study site. Final drug accountability reconciliation will be performed at the subject visit occurring at the end of therapy or at early discontinuation. Unused study drug will be destroyed.

6.4 Dosage Administration

Subjects will be instructed to take study drug (1 tablet of B/F/TAF) orally with at least 8 ounces of plain water once daily in the morning throughout the treatment period. On Day 1, the first dose of the study medication will be administered in clinic after baseline labs have been drawn.

Following initial dosing at Day 1, the study team will provide the subject the remainder of the 30-day study supply to continue on the following day. Subjects will receive additional 30-day supply on Week 4 and Week 8 visits, and 90-day supply on Week 12, 24, and 36 visits.

The study team will be responsible for explaining the correct use of the study drug to the subject, verifying that the instructions are followed properly, maintaining accurate records of study drug dispensing, and collection of all used study drug, including empty drug packaging.

Subjects will be instructed to contact the investigator as soon as possible if a complaint or problem with the study drug exists, so that the situation can be assessed in a timely manner.

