3.2.2 Day 1 Assessments

Screening tests must be available before the subject is eligible for study participation. Once screening is completed and the subject meets all eligibility criteria, the subject will obtain baseline evaluations. Study drug administration may occur after completion of all baseline procedures.

Before Study Drug Administration:

- Review eligibility criteria (see [Section 5](#)) and confirm eligibility of subject.
- Obtain interval medical history.
- Conduct complete physical examination, including weight and vital signs [blood pressure (BP), respiratory rate (R), heart rate (HR), and temperature (T)].
- Collect concomitant medication information.
- Plasma HIV-1 RNA
- Plasma HBV DNA.
- Quantitative HBsAg level.
- CD4 cell count.
- HIV-1 genotype/phenotype, if HIV-1 RNA is ≥ 500 copies/mL.
- HBV genotype and resistance assay, if HBV DNA is ≥ 500 IU/mL.
- Complete blood count.
- Comprehensive metabolic panel.
- Urine pregnancy test for women of childbearing potential.
- FibroScan test (IHV only) – this test may be conducted within 30 days prior to or on the Day 1 Visit.
- Blood for PAXgene DNA and RNA analysis.
- Blood for storage of plasma, serum, and peripheral blood mononuclear cells (PBMC) for future research purposes.

Study Drug Administration (and Post-Study Drug Assessments):

- Administer first dose of B/F/TAF.
- Dispense study drug supply (remainder of 60-day supply).
- Reinforce study drug instruction: subjects are to take one (1) tablet of B/F/TAF once daily upon awakening with at least 8 oz. of plain water, and without regards to food.
- Dispense Study Drug Diary.
- Collect adverse event information.
- Collect concomitant medication information.
- Instruct subject to bring all study drugs and bottles to each future study visits.

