3.2.3 Treatment Assessments

3.2.3.1 Week 4 and 8 Visits (\pm 7 days)

- Obtain interval medical history.
- Conduct targeted physical examination (if needed), including weight and vital signs [BP, R, HR, T].
- Collect concomitant medication information.
- Collect adverse event information.
- Evaluate Patient Diary and number of used and unused tablets.
- Plasma HIV-1 RNA.
- Plasma HBV DNA.
- Quantitative HBsAg level.
- Complete blood count.
- Comprehensive metabolic panel.
- Urine pregnancy test for women of childbearing potential.
- Blood for storage of plasma, serum, and PBMCs.
- Dispense study drug supply (30-day supply for Week 4; 60-day supply for Week 8).
- Reinforce study drug instruction: subjects are to take one (1) tablet of B/F/TAF once daily upon awakening with at least 8 oz. of plain water, and without regards to food.
- Instruct subject to bring all study drugs and bottles to each future study visits.

3.2.3.2 Week 12, 24, and 36 Visits (\pm 2 weeks for Week 12 and Week 36; \pm 4 weeks for Week 24)

- Obtain interval medical history.
- Conduct targeted physical examination (if needed), including weight and vital signs [BP, R, HR, T].
- Collect concomitant medication information.
- Collect adverse event information.
- Evaluate Patient Diary and number of used and unused tablets.
- Plasma HIV-1 RNA.
- Plasma HBV DNA.
- Quantitative HBsAg level.
- CD4 cell count.
- Complete blood count.
- Comprehensive metabolic panel.
- Urine pregnancy test for women of childbearing potential.
- Blood for PAXgene RNA analysis.
- Blood for storage of plasma, serum, and PBMCs.

- Dispense study drug supply (90-day supply).
- Reinforce study drug instruction: subjects are to take one (1) tablet of B/F/TAF once daily upon awakening with at least 8 oz. of plain water, and without regards to food.
- Instruct subject to bring all study drugs and bottles to each future study visits.

Additional Week 24 assessments:

- HBV profile.
- FibroScan test (IHV only). This test may be done during the Week 24 visit, or within 2 weeks (before or after) the scheduled Week 24 visit.

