9.2.2.1 US FDA Snapshot Algorithm for HIV-1 Efficacy Analyses

The analysis window at Week 24 is defined as from Study Day 140 to Day 196. All HIV-1 RNA data collected on-treatment will be used in the snapshot algorithm. HIV-1 Virologic outcome will be defined as the following categories:

- **HIV-1 Virologic Success:** this includes subject who have the last available HIV-1 RNA < 50 copies/mL in the Week 24 analysis window while on study treatment.
- **HIV-1 Virologic Failure:** this includes subjects who
 - a. Have the last available HIV-1 RNA \geq 50 copies/mL in the Week 24 analysis window while on study treatment, or
 - b. Do not have on-treatment HIV-1 RNA data in the Week 24 analysis window and
 - 1) Discontinue study drug prior to or in the Week 24 analysis window due to lack of efficacy, or
 - 2) Discontinue study drug prior to or in the Week 24 analysis window due to reasons other than adverse events (AE), death, or lack of efficacy and have the last available HIV-1 RNA up to 1 day after the premature discontinuation of the study drug \geq 50 copies/mL.
- **No HIV-1 Virologic Data in the Week 24 analysis window:** this includes subjects who do not have on-treatment HIV-1 RNA data in the Week 24 analysis window because of the following:
 - a. Discontinuation of the study drug prior to or in the Week 24 analysis window due to AE or death (regardless of whether the last available HIV-1 RNA up to 1 day after the premature discontinuation of the study drug < 50 copies/mL or not), or
 - b. Discontinuation of the study drug prior to or in the Week 24 analysis window due to reasons other than AE, death, or lack of efficacy (e.g., withdrew consent and loss to follow-up) and the last available HIV-1 RNA up to 1 day after the premature discontinuation of the study drug is < 50 copies/mL, or
 - c. Missing data during the window but remains on study drug.

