9.2.2.2 Missing = Failure Method for HBV Efficacy Analyses

Similarly, the analysis window at Week 24 for HBV DNA outcomes is defined as from Study Day 140 to Day 196. For HBV DNA analysis, this study will use the missing = failure method. HBV virologic outcome will be defined as follows:

- **HBV Virologic Success:** this includes subject who have the last available HBV DNA <29 IU/mL in the Week 24 analysis window while on study treatment.
- **HBV Virologic Failure:** this includes subjects who
 - a. Have the last available HBV DNA \geq 29 IU/mL in the Week 24 analysis window while on study treatment, or
 - b. Do not have on-treatment HBV DNA data in the Week 24 analysis window regardless of reason (e.g. discontinued study drug due to AE, death or lack of efficacy; missed Week 24 visit; withdrew consent for any reason).

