APPENDIX B. PROTOCOL AMENDMENT HISTORY

Version (version date)	Affected Sections	Description of Changes	Brief Rationale
1.1	3.2.2. Day 1 Assessments	Dispense study drug supply from 30-days to up to 60-days	Allow extra study drug to be dispense to subjects on Day 1 to avoid having them ran out before next study visit window.
2.0	5.3 Exclusion Criteria	Clarification on history of malignancy as an exclusion	Allow subjects with history of malignancy that is in remission to be included in this phase 4 study.
3.0	5.2 Inclusion Criteria and Figure 3-1 in Study Schema. Rationale in Section 4. Discussion of Design	Eligibility to allow those with M18V mutation and those who are currently not HIV suppressed to enter the study.	Allows subjects with M184V and M184I mutation or having HIV viral load not suppressed to be included in the study as these does not affect response to B/F/TAF. Rationale added to Section 4. Discussion of Design
4.0	3.1 Study Design, and 3.2 Study Procedures	Change from single center to multicenter study. Fibroscan will only be done in the IHV.	Allow addition of a second site (Philadelphia DOH clinic). Only IHV site has FibroScan to conduct this procedure.

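### Section 6.4 dispenses 30 days of drug at Day 1 and Week 8 where Section 3.2 dispenses 60; with daily dosing and leftovers kept, the 6.4 supply can end on Day 180, before the Week 24 window closes on Day 196

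*Combined protocol and SAP*

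**What the plan says.** Three current sections of the protocol state how much drug to dispense.

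- **Section 6.4, Day 1:** "the study team will provide the subject the remainder of the 30-day study supply to continue on the following day".
- **Section 6.4, later visits:** "Subjects will receive additional 30-day supply on Week 4 and Week 8 visits, and 90-day supply on Week 12, 24, and 36 visits".
- **Section 3.2.2, Day 1:** "Dispense study drug supply (remainder of 60-day supply").
- **Section 3.2.3.1, Weeks 4 and 8:** "Dispense study drug supply (30-day supply for Week 4; 60-day supply for Week 8").

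The two accounts agree at Weeks 4, 12, 24 and 36 (Section 3.2.3.2 also gives 90 days at each of the last three). They disagree at Day 1 and at Week 8, by 30 days each time.

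Appendix B gives the reason for the larger Day 1 supply. Amendment 1.1 raised it in Section 3.2.2: "Allow extra study drug to be dispense to subjects on Day 1 to avoid having them ran out before next study visit window".

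The Week 24 window for HIV-1 RNA is in Section 9.2.2.1: "The analysis window at Week 24 is defined as from Study Day 140 to Day 196". Section 9.2.2.2 sets the same days for HBV DNA: "the analysis window at Week 24 for HBV DNA outcomes is defined as from Study Day 140 to Day 196".

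**The concern.** Section 6.4 is the section on dosing and supply, so staff may well take quantities from it. A site that does so gives 60 fewer tablets before Week 24 than one that follows the visit-by-visit procedures. The problem that amendment 1.1 was written to remove then remains at that site.

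Two things are at stake. The first is patient safety. The study tablet is both the HIV regimen and the HBV treatment, and Section 1.4.8 links a regimen's HBV activity to avoiding hepatitis flares that may threaten life. A patient whose visit is late but within its window could run out of both treatments. The second is the primary analysis. The longest gap falls just before the Week 24 draw that decides both primary endpoints, so a rebound caused by the supply schedule could be counted as failure of the drug.

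**Working it through.** **Inputs**

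- One tablet daily from Day 1 (Section 6.4).
- Visit windows: ±7 days at Weeks 4 and 8; ±2 weeks at Weeks 12 and 36; ±4 weeks at Weeks 24 and 48 (Sections 3.2.3.1 to 3.2.3.3).
- Quantities dispensed as listed in Sections 6.4 and 3.2.
- Assumptions: Week n falls on Day 7n, leftover tablets stay with the patient, and a gap is the number of doses missed before the visit day.

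**The plan's own window.** 24 × 7 = 168, and 168 ± 28 gives Days 140 to 196. This matches Sections 9.2.2.1 and 9.2.2.2 and supports the day numbering used here.

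**Supply before Week 24**

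- Section 6.4: 30 + 30 + 30 + 90 = 180 tablets, so the last dose is on Day 180.
- Section 3.2: 60 + 30 + 60 + 90 = 240 tablets, so the last dose is on Day 240.

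**Gap at the latest permitted visit, with earlier visits nominal.** Let T be the tablets dispensed before the visit and L its latest day. Missed doses = max(0, L − 1 − T).

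| Visit | L | T, 6.4 | Missed, 6.4 | T, 3.2 | T, 6.4 with Day 1 = 60 | T, 6.4 with Week 8 = 60 |
|---|---|---|---|---|---|---|
| Week 4 | 35 | 30 | 4 | 60 | 60 | 30 |
| Week 8 | 63 | 60 | 2 | 90 | 90 | 60 |
| Week 12 | 98 | 90 | 7 | 150 | 120 | 120 |
| Week 24 | 196 | 180 | 15 | 240 | 210 | 210 |
| Week 36 | 266 | 270 | 0 | 330 | 300 | 300 |
| Week 48 | 364 | 360 | 3 | 420 | 390 | 390 |

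Under 6.4, a Week 24 draw on Day 182 follows one missed dose (Day 181). A draw on Day 196 follows 15 (Days 181 to 195).

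Under Section 3.2, and under 6.4 with only Day 1 raised to 60, T exceeds L at every visit, so no permitted visit day has a gap. A day-by-day count over all 729 combinations of earliest, nominal and latest visits (3 to the power 6) found none for either. Raising only Week 8 closes the gaps from Week 12 onward but leaves 4 doses at Week 4 and 2 at Week 8.

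**Every visit at its latest day, 6.4.** Doses missed before the earlier visits leave tablets for later, and the Week 12 supply starts on Day 98. The supply then lasts to Day 187 if each visit-day dose comes from the new supply, or to Day 188 if it is skipped when stock is empty. A Day 196 draw follows 8 or 7 missed doses.

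**Imperfect adherence, 6.4.** With k doses missed before Day 180, the Day 196 gap is max(0, 15 − k). It vanishes at k = 15, which is 180 of 195 doses taken, or 92.3%.

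**If all leftovers were returned at every visit**

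- *Week 4:* 6.4 still leaves 4 missed doses before Day 35. Section 3.2 leaves none.
- *Week 12:* under 6.4, 30 tablets from Day 56 last to Day 85, so Days 86 to 97 are missed (12 doses). Under Section 3.2, 60 tablets last to Day 115, so there is no gap.
- *Week 24:* both schedules rest on the same 90 tablets from Day 84, which end on Day 173. A Day 196 draw follows 22 missed doses (Days 174 to 195) either way.

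**The case against.** The strongest objection is about leftovers. Section 6.3.3 has patients return unused drug at some visits without naming them. If leftovers were surrendered at Week 12, the Week 24 supply would be the same under both schedules, and aligning 6.4 would not close the late Week 24 gap. This stands as a limit: the Day 180 result, and the full coverage under Section 3.2, both need leftovers to be kept. It does not remove the contradiction, because on the full-return reading the 6.4 quantities still produce gaps at Weeks 4 and 12 that Section 3.2 avoids.

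The Week 24 gap also needs several things together: a site that follows 6.4 for both Day 1 and Week 8, a visit about two weeks or more past nominal, near-complete adherence, and no response to the tablet count. Section 3.2.3 requires staff at each visit to "Evaluate Patient Diary and number of used and unused tablets", so a site could see the shortfall coming and resupply. Each of these points is fair. They bear on how often a gap would occur, not on whether the text is wrong.

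The clinical effect is uncertain too. Section 1.2.3.3 gives a hepatocyte half-life of 150 to 180 hours for tenofovir diphosphate, so 15 days (360 hours) is only 2.0 to 2.4 half-lives. That tempers the HBV concern without excluding rebound. It offers no reassurance for bictegravir, whose listed half-life is 17.3 hours.

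Finally, amendment 1.1 concerns Day 1 only. Nothing shows independently that 60 is the intended figure at Week 8. That is correct, and the case for Week 8 is consistency with Section 3.2.3.1.

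**Conclusion.** The error is real. Two operative quantities in Section 6.4 contradict Sections 3.2.2 and 3.2.3.1, and for Day 1 the amendment's rationale shows that the larger figure is intended. The finding rests on the conflict between current sections, not on a difference from the amendment log.

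With daily dosing, leftovers kept and earlier visits nominal, following 6.4 leaves up to 15 missed doses before a permitted Week 24 draw, with shorter gaps at Weeks 4, 8, 12 and 48. With every visit at its latest day the Week 24 gap is 7 or 8 doses. Visits on nominal days have no gap, and sites following Section 3.2 have none on any permitted day.

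The documents give no basis for estimating how many patients would be affected or how far Week 24 response would change. This should be corrected because it can interrupt treatment close to the primary measurement, but it does not invalidate the design.

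**What to change.** Change Section 6.4 to 60 days at Day 1, 30 at Week 4, 60 at Week 8, and 90 at Weeks 12, 24 and 36. The Day 1 change closes every gap when leftovers are kept. The Week 8 change makes the sections agree, and it also covers a late Week 12 visit if leftovers are returned.

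Separately from the contradiction, it would help to state in Section 6.3.3 that unused tablets counted at interim visits stay with the patient, since coverage to Day 196 depends on this.

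The cost is two numbers in the text. For a site that was following 6.4, the supply rises from 360 to 420 tablets, that is 60 more per patient, or two 30-tablet bottles (bottle size from Section 6.3.1). For 60 patients the maximum is 60 × 60 = 3,600 tablets, or 120 bottles. Section 3.2 already provides for this quantity.

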6.5 Blinding

This is an open-label noncomparative study. Both the subject and study personnel with direct contact with the subject will know the study treatment that is administered.

6.6 Concomitant Medications

Drug interaction studies have been conducted with B/F/TAF or its components. A complete summary of the pharmacokinetic effects of other drugs on B/F/TAF or its components are found in the BIKTARVY® package Insert ([Biktarvy 2018](#)).

Bictegravir is a substrate of CYP3A and UGT1A1. BIC is also an inhibitor of the organic transporter 2 (OCT2) and multidrug and toxin extrusion transporter 1 (MATE1) in vitro, such that coadministration of BIC with drugs that are substrate of OCT2 and MATE1 (e.g. dofetilide) may increase their plasma concentration. On the other hand, TAF is a substrate of P-glycoprotein (P-gp) and breast cancer resistance protein (BCRP), thus, coadministration of drugs that inhibit these enzymes may increase the absorption and plasma concentration of TAF. TAF is not an inhibitor of drug transporters P-gp, BCRP, renal transporter MATE1 or OCT2. At clinically relevant concentrations, both BIC and TAF are not an inhibitor of hepatic transporters OATP1B1, OATP1B3, OCT1, BSEP, renal transporters OAT1, OAT3, or CYP (including CYP3A) or UGT1A1 enzymes. A list of prohibited medications are listed in **Table 6-1**.

Table 6-1: List of Prohibited Medications

Drug Class	Prohibited Agents [#]
Antiarrhythmic Agent	Dofetilide
Anticonvulsants	Phenobarbital, Phenytoin, Carbamazepine, Oxcarbamazepine
Antimycobacterials	Rifampin, Rifapentine
GI Motility Agents	Cisapride
Herbal/Natural Supplements	St. John's Wort, Echinacea
Miscellaneous Agents	Mitotane

[#] Administration of any of the above medications must be discontinued at least 30 days prior to the Day 1 visit and for the duration of the study.

